#### **6.4.4 Criteria for Early Termination of Individual Subjects**

Subjects may withdraw their consent to participate in the study at any time.

If a subject withdraws consent, the date and reason for consent withdrawal should be documented. Subjects will be encouraged to remain in the clinic for safety assessments until the Investigator deems that it is safe for the subject to be discharged. Subject data will be included in the analysis up to the date of the consent withdrawal.

- AE or SAE that requires discontinuation at the discretion of the Investigator
- Protocol violation: If protocol violation or concurrent illness occurs, which, in the clinical judgment of the Investigator or after discussion with the Sponsor, may invalidate the study by interfering pharmacokinetically or pharmacodynamically with the investigational products, subject will be withdrawn by the Investigator.
- Lost to follow-up. The subject did not return to the clinic and attempts to contact the subject were unsuccessful. Attempts to contact the subject must be documented.
- Voluntary withdrawal of consent (mandatory removal from study)
- Discretion of Investigator (document reason on CRF)
- Subject becomes pregnant or begins breastfeeding (mandatory)
- Study discontinuation by Sponsor

Wherever possible, the tests and evaluations, including those listed for the Follow-up Visit should be performed for all subjects who discontinue prior to the completion of the study.

In the event the Investigator determines to terminate a subject participation in the Clinical Study, the Investigator must notify the Sponsor of such decision and rationale immediately in writing. In all cases, the appropriate IRB/IEC and other applicable regulatory authorities shall be informed.

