## 6.0 STUDY DESIGN AND DESCRIPTION

### 6.1 Study Design

This is a randomized, placebo-controlled, multiple-ascending dose study to investigate the safety, tolerability, PK and PD of SC administration of HM15211, conducted in 1 part.

[figure not shown]
This study will be single-blind and conducted in up to 6 cohorts comprising a total of up to 72 obese subjects with NAFLD. Each cohort will enroll subjects to ensure that at least 12 subjects per cohort will complete the study. Subjects will be randomized to investigational product (IP) or placebo in a 3:1 ratio via an Interactive Web Response System (IWRS). Per cohort (n=12 subjects), 9 subjects will be randomized to IP and 3 subjects to placebo. Cohorts may partially overlap after at least 9 subjects have completed 2-4 weeks of treatment (2 weeks of treatment is reached at Visit week 3) and a dose escalation decision has been made. Study drug will be administered weekly over a period of 12 weeks.

Based on available safety, tolerability, and PK data of each cohort, and following a safety review and dose escalation meeting between the investigator and the sponsor, dose escalation to the next cohort may proceed. Cohorts will start in sequential order but may overlap partially during execution. Replacement of dropouts and withdrawals may take place.

[figure not shown]
Each subject will undergo a screening visit, 2 in-house/ treatment periods and multiple outpatient visits. A final follow-up visit that will conclude subject study participation.

The duration of participation in this study including Screening, Treatment and Follow-up will be approximately 23 weeks for each subject including 12 weeks of treatment period.

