### **12.2.1 Analysis Sets**

#### **12.2.1.1 Safety Set**

The Safety analysis set will include all subjects who received study medication (HM 15211 or Placebo). The Safety analysis set will be used for demographic, baseline characteristics and safety summaries.

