#### **12.2.1.2 Pharmacokinetic (PK) Analysis Set**

The PK analysis set will include all subjects who received HM 15211 or placebo with sufficient evaluable PK data appropriate for the evaluation of interest (without major protocol deviations or violations that would have an impact on the absorption, distribution, metabolism, or excretion of HM 15211). The PK analysis set will be used for analysis of PK endpoints.

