#### **12.2.1.3 Pharmacodynamics (PD) Analysis Set**

The PD analysis set will include all subjects who received HM 15211 or placebo with sufficient evaluable PD data appropriate for the evaluation of interest (without major protocol deviations or violations that would have an impact on the PD of HM 15211). The PD analysis set will be used for analysis of PD endpoints.

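### Section 6.4.4 compels withdrawal over possible PK/PD interference without separating stopping study drug from leaving the study, so scheduled safety and imaging observation ends for a concern the PK and PD sets already largely handle

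*Protocol*

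**What the plan says.** Section 6.4.4 of the protocol lists the grounds for early termination of individual subjects. One bullet begins "If protocol violation or concurrent illness occurs, which, in the clinical judgment of the Investigator or after discussion with the Sponsor", and continues that the event "may invalidate the study by interfering pharmacokinetically or pharmacodynamically with the investigational products, subject will be withdrawn by the Investigator". The section then describes what follows: "In the event the Investigator determines to terminate a subject participation in the Clinical Study", the Sponsor is notified. It also contains a backstop: "Wherever possible, the tests and evaluations, including those listed for the Follow-up Visit should be performed for all subjects who discontinue" before completing the study.

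Three analysis sets bear on this:
- The PK set (12.2.1.2) takes dosed subjects with sufficient evaluable data, "without major protocol deviations or violations that would have an impact on the absorption, distribution, metabolism, or excretion of HM 15211".
- The PD set (12.2.1.3) has the parallel condition, "without major protocol deviations or violations that would have an impact on the PD of HM 15211".
- The Safety set (12.2.1.1) has no such condition: "The Safety analysis set will include all subjects who received study medication".

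On replacement, Section 6.1 states: "Replacement of dropouts and withdrawals may take place". It sets a target of at least 12 completers per cohort, and Section 8.6 continues randomization until that number is reached.

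**The concern.** The ground for this withdrawal is the validity of PK or PD data. Adverse events that call for discontinuation have a separate bullet. Yet the consequence is written as the end of participation, so safety observation stops together with the PK and PD data that gave rise to the concern.

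That matters because Section 5.1.1 places adverse events, immunogenicity, ABPM, Holter and MRI-PDFF liver fat among the primary endpoints, with nine active subjects per dose. If the events that lead to withdrawal are partly consequences of the drug, observation is shortened in subjects who tolerate it poorly. Their replacements enter the late-treatment summaries only if they themselves reach those visits.

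**Working it through.** The protocol states no figure on this point, so the check sets its sections side by side.

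**1. Treatment or study?** The heading of 6.4.4 and its reference to a subject's participation both point to leaving the study. No sentence keeps these subjects on the schedule. By contrast, Section 9.1.10 withdraws a pregnant subject but encourages her to complete post-treatment follow-up.

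**2. Overlap with the analysis sets.** A major violation that affects PK or PD already removes the subject from the relevant set. Two parts of the 6.4.4 trigger go further: concurrent illness, which neither definition names, and interference that is only possible, whereas the sets require an impact.

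**3. What observation is lost.** Scheduled days for cohort 1-4 and up, counting Days 77 to 82 singly, after Day 29 are 36, 43, 50, 57, 64, 71, 77, 78, 79, 80, 81, 82, 85, 99 and 113, which is 15 days. After Day 15, Days 22 and 29 are added: 17. After Day 57, the first four (36 to 57) drop out: 15 − 4 = 11. Post-dose antibody samples fall on Days 22, 50, 78, 85 and 99 (9.1.20). The second ABPM/Holter period is Days 77 or 78 to 82 (6.2, 9.1.14). Post-baseline MRI-PDFF is in weeks 8 and 12 (9.1.18). The withdrawal days below are assumptions.

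| Withdrawn after | Scheduled days left | Antibody samples left (of 5) | Second ABPM/Holter period | MRI-PDFF left (of 2) |
|---|---|---|---|---|
| Day 15 | 17 | 5 | not reached | 2 |
| Day 29 | 15 | 4 | not reached | 2 |
| Day 57 | 11 | 3 | not reached | 1 |

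**4. What the backstop recovers.** The only visit it names is the Follow-up Visit. Sections 9.1.20, 9.1.14 and 9.1.18 schedule no antibody sample, ABPM or MRI for Day 113, and injection-site inspection ends on Day 85 (9.1.21). A single discontinuation visit can yield laboratory tests, an ECG and an examination. It cannot recreate serial antibody samples or recordings around the twelfth dose.

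**5. Link to tolerability.**
- Appendix B, item 4, calls nausea and vomiting anticipated. It raises antiemetics at G2 and gives them as indicated at G3 and G4. Section 6.4.1 makes emesis the main tolerability criterion.
- Table 7-1 prohibits antiemetics, giving an effect on GI motility as the reason, and Section 7.3 extends the prohibition to the end of the study.
- Appendix B, item 2, raises prednisone for skin events at G2 and starts it at G3. Table 7-1 prohibits corticosteroids that are oral or systemic long-acting. It is unclear whether the long-acting qualifier also limits the oral ones, but the antiemetic conflict does not depend on that.

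So following Appendix B for a drug-related event can mean using a prohibited medicine that is listed for a pharmacodynamic reason. That can meet the 6.4.4 trigger if the Investigator or Sponsor sees it so.

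**6. Scale, under assumptions.** Each active subject is 1/9 = 11% of a dose group. The chance of seeing at least one case of an event with true rate p among n subjects is 1 − (1 − p)^n. The rates are assumed:

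| p | n = 9 | n = 8 |
|---|---|---|
| 5% | 0.370 | 0.337 |
| 10% | 0.613 | 0.570 |
| 20% | 0.866 | 0.832 |
| 30% | 0.960 | 0.942 |

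The drop is about 2 to 4 percentage points per subject. This is a ceiling: it supposes an event that could arise only after withdrawal, with nothing recovered and nobody replaced. It does not measure selection.

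**The case against.** The rule is narrower than a quick reading suggests. A reader might infer that any violation or illness forces a subject out. It does not: the event must be thought capable of invalidating the study, in the Investigator's view or after discussion with the Sponsor. This stands.

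A reader might also infer that the rule achieves nothing, since the sets exclude the data anyway. That is too strong. Withdrawal also ends exposure and opens a place for replacement, which an analysis-set exclusion does not. PK and liver fat are themselves primary objectives, and PK data feed the escalation decisions. Concurrent illness is outside the wording of both sets.

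Nor is safety information simply cut off. Data up to withdrawal remain in the Safety set, adverse events are followed to resolution or until follow-up is considered unnecessary (10.6), and the backstop asks for assessments where possible. The loss is partial.

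It is tempting to express the loss as a widening zero-event bound, 1 − 0.05^(1/n), which goes from 28% at n = 9 to 39% at n = 6. The documents do not support that as an estimate. It treats withdrawn subjects as contributing nothing, ignores replacement, and needs a number of withdrawals that the protocol does not give.

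Finally, MRI-PDFF is analysed as a PD parameter (12.2.4), so a scan obtained after PD interference may still be excluded. It would be usable where the concern is PK only, and otherwise available for a supportive summary.

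What these replies leave unanswered is why a data-validity concern should end scheduled safety visits, and how withdrawal for prohibited medication fits with Appendix B.

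**Conclusion.** The point holds in limited form. Section 6.4.4 joins a PK/PD data concern to leaving the study. For major violations it adds little to what the PK and PD sets already do, and it gives up scheduled antibody, week-12 ABPM/Holter and imaging observation that the backstop does not replace. Because the trigger can follow from treating a drug-related event, and because withdrawals may be replaced, late-treatment safety summaries by dose may lean toward subjects who tolerate the drug.

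The direction of that selection rests on the Appendix B and Table 7-1 conflict leading to withdrawals in practice. The protocol permits this but does not make it automatic. The size is unknown, because no withdrawal rate is given. The day counts in the table are maximum losses per subject, less whatever is done at discontinuation. The change is worth making because it is cheap and safety is a primary objective. Whether dosing should continue in such a subject is a clinical matter on which no view is taken here.

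**What to change.** 1. In Section 6.4.4, state that a subject who meets this bullet is, with consent, kept in the study for the remaining scheduled safety, immunogenicity and imaging assessments to Day 113, whether or not study drug is stopped. Leave the decision on study drug as it is.
2. State that the affected PK/PD data are flagged for exclusion, and name concurrent illness in Sections 12.2.1.2 and 12.2.1.3 so that the set definitions cover the whole trigger.
3. Reconcile Section 6.4.4 and Table 7-1 with Appendix B, so that it is clear whether treating an adverse event as Appendix B suggests counts as a violation under this bullet.

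The cost is a few sentences, plus visits and samples that are already on the schedule. The downside is that some of these will be spent on subjects whose PK/PD data are later excluded, in addition to any replacements enrolled.

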## 7.0 STUDY POPULATION

### 7.1 Inclusion Criteria

Subjects who meet all criteria at Screening will be included in the study:

1. Adults  $\geq 18$  to  $\leq 65$  years.
2. Body mass index (BMI)  $\geq 30 \text{ kg/m}^2$ , with stable body weight by history for 3 months (defined as change  $< 5\%$ ).
3. Waist circumference  $\leq 57$  inches.
4. Fasting Plasma Glucose  $< 7 \text{ mmol/L}$  (126 mg/dL).
5. HbA1c  $< 6.5\%$ .
6. CAP  $\geq 300 \text{ dB/m}$  by FibroScan. (Subjects with matching results within 30 days prior to screening don't need to undergo this procedure). Subjects with CAP 275-299 dB/m may proceed to MRI with CRO approval pending review of medical history and lab data.
7. Liver fat by MRI-PDFF  $\geq 10\%$ .
8. Female subjects must be non-pregnant and non-lactating. Females of child bearing potential must use highly effective contraceptive methods, stable at least 2 months prior to the screening. Male subjects must be surgically sterile, abstinent or if engaged in sexual relations of child-bearing potential, the subject and his partner must use an acceptable method of contraception.
9. Ability and willingness to comply with all protocol procedures (e.g., correct handling of investigational product, compliance to visit schedule and dietary advice, and complete trial-related questionnaires).

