| Summary of Study Design | 
The study includes a randomized, single-blind, placebo-controlled, multiple-ascending dose study to investigate the safety, tolerability, and PK of SC administration of HM15211 in approximately up to 72 (n=12/cohort) obese subjects with NAFLD.
 
To assess the effect of multiple SC doses of HM15211 in obese subjects on:
 

1. Change in % liver fat, assessed by MRI-PDFF in obese subjects with pre-existing % liver fat >10% (determined by MRI-PDFF).

 
The study will be conducted in up to 6 dosing cohorts that might partially overlap, enrolling 12 subjects per cohort. Subjects will be randomized to HM15211 or placebo in a ratio of 3:1 (9 on active, 3 on placebo).
 
Dose escalation to the next dose will proceed based on safety and tolerability and available PK data. After 2-4 weeks treatments of at least 3/4 (n=9) active participating subjects of previous dose, safety and available blinded PK/PD data will be reviewed to decide on beginning the next cohort. If dose escalation is stopped, dose de-escalation may occur in additional cohorts, to further refine clinically relevant dose levels.
 
Screening:
 
A Screening Visit will be performed up to 44 days prior to the first dosing to identify subjects for the study. All screening evaluations except MRI-PDFF will be performed.
 
Only eligible subjects will undergo an MRI-PDFF for the assessment of liver fat within 30 days of randomization. Subjects who meet the inclusion criteria of >10% liver fat will proceed with the study and will be invited for the In-house Period 1.
 
For subjects in cohort 1-5 and up: Only eligible subjects will undergo an MRI/MRI-PDFF for the assessment of liver fat and visceral fat within 30 days of randomization. Subjects who meet the inclusion criteria of >10% liver fat will proceed with the study and will be invited for the In-house Period 1.
 
In-house Period 1:
 
Day -2: Subjects will check in to the clinic in the morning on Day -2 for a 10-day In-house Period. They will receive standardized meals throughout their inpatient stay. Subjects will be connected to an ABPM system, and overnight measurements will be taken to
 |
|--------------------------------|--|

|  |   |
|--|---|

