### 5.1.2 Exploratory Objectives and Endpoints

To assess additional PD properties of HM15211 after multiple SC doses in comparison to placebo by:

- Incretins / metabolic hormones
  - Glucagon-like peptide-1 (GLP-1)
  - Gastric inhibitory peptide (GIP)
  - Glucagon
  - Fibroblast growth factor 21 (FGF21)
  - Leptin
- Body weight and body mass index (BMI)
- Waist circumference
- Serum lipid profile and particles
  - Total cholesterol
  - Low-density lipoprotein (LDL), LDL-C, LDL-P (particles),
  - High-density lipoprotein (HDL), HDL-C, HDL-P (particles)
  - Very low-density lipoprotein (VLDL), VLDL-C, VLDL-P (particles)
  - Triglyceride
  - Free Fatty Acids (FFAs)
- Amino acid profile
- Inflammatory marker
  - Adiponectin
- Bone metabolism parameters
  - Fasting carboxy-terminal crosslinked telopeptide of type 1 collagen (CTX-1)
  - Osteocalcin (OC)
  - Procollagen type 1 N-terminal propeptide (P1NP)
- Glucose metabolism parameters:
  - Fasting plasma glucose (FPG)
  - Fasting insulin, fasting C-peptide
  - HbA1c
- Ketone bodies
  - Beta-hydroxybutyrate

---

- Changes in liver steatosis and liver stiffness assessed by FibroScan® (VCTE), determined as absolute and percent change from baseline in controlled attenuation parameter (CAP) and liver stiffness measurements (LSM)
- Changes in visceral fat volume, determined by absolute and relative percent change assessed by MRI imaging

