### Screening Visit:

Before the screening takes place, potential subjects for the trial will be provided with written and oral information about the trial and the procedures involved. Subjects must sign the informed consent form (ICF) prior to entering the study. Please see section [9.1.1](#) for further details.

The screening visit will be performed up to 44 days prior to the first dosing day, to identify eligible subjects for the study. All assessments performed at the screening visit are stated in [Table 16-1](#) and will be recorded in the electronic case report form (eCRF). Please see section [9.1.2](#) and [11.2](#) for further details.

Subjects' screening lab parameters and VCTE (CAP) scores will be evaluated to identify subjects who are likely to have a liver fat content of > 10% at MRI-PDFF. Depending on the outcome/results of these values, the subjects will proceed to MRI/MRI-PDFF. For further details on parameters and outcome for the determination to proceed to MRI/MRI-PDFF see the Operations Manual. Subjects who are not able to proceed to MRI-PDFF will be recorded as screening failures.

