#### **9.1.19 VCTE**

One-dimensional vibration controlled transient elastography (VCTE) assessed via eg, FibroScan (EchoSensTM, Paris, France) will be used in this study.

At Screening, subjects will be examined with the FibroScan to assess the controlled attenuation parameter (CAP) in order to qualify for the inclusion in the study.

For subjects participating in cohort 1-4 and up, FibroScan assessments will be performed on Day 85 to assess a change from baseline in CAP and LSM.

It is a device, that uses non-invasive, one-dimensional vibration controlled transient elastography (VCTE). The device generates a low-frequency shear wave from a probe applied to the subject's skin between the ribs. The speed of the wave spread is then measured between two points within the liver to allow the livers stiffness to be

quantified. The wave will travel more rapidly through stiff tissue. An examination using the FibroScan consists of ten signal acquisitions at a single point; the whole process lasts around 15 minutes. The results are instantly displayed on a screen and the value for stiffness can be matched to a fibrosis stage.

For details please see the Operations Manual.

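### The FibroScan waiver in criterion 6 can leave cohorts 1-4 onward without a study baseline for change in CAP and liver stiffness

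*Protocol*

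**What the plan says.** Criterion 6 appears in the same form in the Study Summary (Section 2.0) and in Section 7.1. It requires a CAP of at least 300 dB/m by FibroScan, with a route to MRI at 275-299 dB/m on CRO approval. It then waives the scan for subjects who already have a result: "Subjects with matching results within 30 days prior to screening don't need to undergo this procedure". The waiver has no exception by cohort.

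Section 9.1.19 (VCTE) gives the Screening scan one purpose: "subjects will be examined with the FibroScan to assess the controlled attenuation parameter (CAP) in order to qualify for the inclusion in the study". This sentence carries no condition. For cohorts 1-4 onward the same section adds a second use: "FibroScan assessments will be performed on Day 85 to assess a change from baseline in CAP and LSM". Section 5.1.2 and Table 12-1 list the absolute and percent changes in both measures as exploratory endpoints.

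On timing, Section 6.2 states: "The screening visit will be performed up to 44 days prior to the first dosing day". The VCTE rows of Tables 16-4 and 16-5 show a single pre-dose entry, at Screening.

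MRI-PDFF is handled more tightly. Section 2.0 says: "Only eligible subjects will undergo an MRI-PDFF for the assessment of liver fat within 30 days of randomization". Section 9.1.18 names the screening MRI-PDFF as the baseline value and requires standardized acquisition and a central reader.

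**The concern.** While FibroScan was only an entry test, accepting a recent outside result cost nothing. Amendment 4 added the Day 85 scan and the change endpoint for cohorts 1-4 onward. The pre-dose scan thereby became half of a change score, and the waiver stayed as it was.

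For a waived subject, three things are then uncontrolled: how old the baseline is, whether it was taken under study conditions, and whether LSM was captured at all. Criterion 6 and the stated purpose of the Screening scan both mention CAP only, so an outside report giving CAP alone would satisfy the waiver. An LSM that was never recorded, or a study scan that was never done, cannot be recovered at analysis.

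The cohorts are small, at 9 active and 3 placebo subjects each, so each missing or ill-matched baseline weighs more than it would in a large trial.

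**Working it through.** The protocol states no figure for the interval from scan to dose, so there is none to reproduce. The check is interval arithmetic on the protocol's own windows, followed by a comparison of the sections.

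**Inputs**
- Waiver: result up to 30 days before screening (Section 7.1, criterion 6).
- Screening: up to 44 days before first dose (Section 6.2). The schedules run from Day -1 to Day 1 with no Day 0, and Section 6.2 counts the 44 days back from first dosing.
- Day 85 falls 85 - 1 = 84 days after Day 1, with a visit window of ±2 days (Table 9-4).
- Cohort size: 9 active + 3 placebo (Table 4-1).

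**Longest interval permitted**

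| | With waiver | Scan done at Screening |
|---|---|---|
| Scan to first dose | 44 + 30 = 74 days | 44 days |
| Scan to Day 85 | 74 + 84 = 158 days | 44 + 84 = 128 days |
| Scan to Day 85 + 2 | 74 + 86 = 160 days | 44 + 86 = 130 days |
| Share before any treatment (to Day 85) | 74/158 = 47% | 44/128 = 34% |

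The waiver therefore adds at most 30 days. If screening is as late as Day -3, the oldest acceptable outside scan is 3 + 30 = 33 days before dosing. The 74 days is an outer bound, not a typical value.

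**Subjects who could be affected**

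Cohorts 1-4, 1-5 and 1-6, if all are run: 3 × 12 = 36 subjects, of whom 3 × 9 = 27 are active and 3 × 3 = 9 placebo. The protocol gives no basis for estimating how many would use the waiver.

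**The sections side by side**
1. Section 9.1.19: every subject is scanned at Screening. Criterion 6: some need not be. Both cannot hold for a waived subject.
2. Section 9.1.19 requires a change in CAP and LSM at Day 85. The only scheduled pre-dose scan is the one that criterion 6 allows a subject to skip.
3. Section 9.1.18 names the MRI-PDFF baseline. Section 9.1.19 names none for VCTE. The Screening scan takes that role only because no other pre-dose scan is described.
4. Nothing in the protocol text requires a prior result to contain LSM.

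**The case against.** Several points on the other side are fair.

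- **LSM is probably available in many cases.** Section 9.1.19 itself describes FibroScan as measuring shear-wave speed so that stiffness can be quantified, with results shown at once. An outside examination may well have produced an LSM. This stands as far as it goes, but the protocol does not require that value to exist in the report or to be entered.
- **Device and operator.** A reader might infer that waived baselines come from a different machine or operator. The protocol does not say where prior results originate, and it does not fix device or operator for study scans either, at up to 8 sites. This is a possibility, not a demonstrated difference.
- **Selection on a high CAP.** A reader might also infer that the waiver inflates the apparent fall in CAP through regression to the mean. The documents do not support tying that effect to the waiver. It arises whenever the qualifying scan is also the baseline, which is equally so for subjects scanned at Screening and for placebo subjects. Scanning everyone at Screening would not remove it for those who qualify on that scan. No magnitude is claimed here.
- **Drift is limited.** Criterion 2 requires stable weight by history for 3 months, and the waiver adds no more than 30 days to a gap that may already be 44. This reduces the timing concern without removing it.
- **Baseline rules belong in the SAP.** Section 12.1 leaves analysis variables and missing data to the SAP, which is not at hand. A SAP can choose among recorded values but cannot supply a scan or an LSM that was not obtained. Section 9.1.19 also refers details to an Operations Manual that is not shown. That manual may address the gap, but criterion 6 would still contradict Section 9.1.19.

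**Conclusion.** The point holds as a conflict within the protocol with a limited consequence. Criterion 6 allows a subject in cohorts 1-4 onward to have no study FibroScan before dosing, although Section 9.1.19 says that the scan is done and the Day 85 endpoint depends on it. The baseline can then be up to 74 days before first dose instead of 44, and 158 days before Day 85 instead of 128, with no assurance that LSM is present.

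The interval figures are exact from the stated windows. That the Screening scan serves as the VCTE baseline is inferred from its being the only pre-dose scan described. Missing LSM and non-study acquisition are possibilities of unknown frequency. The effect is confined to one exploratory endpoint in a study without hypothesis testing (Section 6.3). Liver fat by MRI-PDFF, a primary endpoint, has its own named baseline and is unaffected. The change is worth making but is not critical.

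**What to change.** In Sections 2.0 and 7.1, limit the waiver for cohorts 1-4 onward: a prior FibroScan result may be used to pre-qualify a subject but does not replace the Screening scan. In Section 9.1.19, state that the Screening FibroScan is performed before dosing in these cohorts, that both CAP and LSM are recorded, and that it is the VCTE baseline, in parallel with the MRI-PDFF wording in Section 9.1.18. This brings the maximum scan-to-dose interval from 74 to 44 days and closes the LSM gap.

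For subjects already enrolled under the waiver, flag the source and date of the baseline scan, and present the CAP and LSM change with and without them. Simply excluding them is less attractive with 9 active subjects per cohort.

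The cost is wording in three places, eCRF entries for LSM and for scan source and date, and a short non-invasive examination for subjects who would otherwise have been waived. Section 9.1.19 puts it at around 15 minutes. The examination is already in the schedule of events.
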